4.3.2.3.1 GIR_{max}

GIR_{max} will be the maximum GIR readings from time 0 to time 300 minutes.

- In a “No Peak” case, this will be set as missing.

4.3.2.3.2 Terminal Rate Constant λ

Terminal rate constant λ is needed before we estimate AUC_{0-t} . It is estimated by:

- a. Find the GIRs after GIR_{max} (section 4.3.2.3.1)
 - i. If there only 1 or 0 available GIR reading after GIR_{max} , then λ will be set as missing.
- b. Do a regression of log-transformed GIR vs Time
- c. λ is the slope from this regression
- d. In a “No Peak” case, λ will be set as missing

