Secondary Endpoints 1:	
Mean differences (within treatments over time and between treatments at specified time points) in:
 
 Time-to-Maximum Glucose Infusion Rate (GIR) ($t_{max(GIR)}$) Time to half-maximal GIR, both early and late ($t_{50(GIR),early}$ & $t_{50(GIR),late}$) Onset of action as measured by a drop of blood glucose (BG) by 5 mg/dL Duration of insulin action (calculated the same as MRT for PK) GIR_{max} Area under the GIR curve ($AUC_{0-t(GIR)}$), both absolute and as a percentage of total $AUC_{0-\infty}$ and Coefficient of Variation (CV) of $AUC_{0-t(GIR)}$, where $t = 5, 10, 15, 20, 30, 45, 60, 90, 120, 150, 180, 210, 240,$ and 300 min 
Other PD parameters may also be calculated.

Secondary Objective 2:	To assess pharmacokinetic (PK) parameters within and across treatments following subcutaneous delivery using Achilles vs Teflon control set on DOI and days 3, 5, and 7 post insertion.
Secondary Endpoints 2:	
Mean differences (within treatments over time and between treatments at specified time points) in:
 
 • Early exposure ($AUC_{0-60min}$) • Mean-residence time (MRT) of insulin • Maximum Insulin concentration (C_{max}) • Time-to-Maximum Insulin Concentration (t_{max}) • Time-to-50% Maximum Insulin Concentration [$t_{50,early}$ & $t_{50,late}$], both early (i.e. before C_{max}) and late (i.e. after C_{max}) • $AUC_{(0-t)}$ (both absolute and as a percentage of $AUC_{(0-300)}$) and Coefficient of Variability (CV) $AUC_{(0-t)}$ where $t = 3, 6, 9, 12, 15, 20, 25, 30, 35, 40, 45, 50, 60, 70, 80, 90, 105, 120, 150, 180, 210, 240$ and 300 min 
Other PK parameters may also be calculated.

Secondary Objective 3:	To assess continuous glucose monitoring (CGM) data, comparing data within and across treatments.
Secondary Endpoints 3:	
 • Mean daily time in range (70-180 mg/dL), DOI through Day 7 inclusive • Mean daily time in target (70-140 mg/dL), DOI through Day 7 inclusive • Mean and median daily glucose, DOI through Day 7 inclusive • Glucose variability (%CV), DOI through Day 7 inclusive • Mean daily time ≤ 70 mg/dL, < 54 mg/dL, DOI through Day 7 inclusive • Mean daily time > 140 mg/dL, > 180 mg/dL, > 240 mg/dL, DOI through Day 7 inclusive • Other CGM metrics may also be calculated
Secondary Objective 4:	To assess performance of investigational infusion set on DOI through 7 for each treatment

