4.3.2 Efficacy Variables

4.3.2.1 Handling of (Possible) Multiple Peaks of GIR and Insulin Curve.

We expect the GIR and insulin curve to have a single peak. However, it is possible that multiple peaks or no peak will be observed. The following are ways to handle GIR curves:

1. Determination of single peak/no peak/Multi-peak will be based on the plot of the GIR/insulin curve
 - a. The statistician will make the judgement based the visual observation of each plot of the GIR/insulin curve
2. No peak. (i.e. the variables keeps rising up to 300 minutes)
 - a. The Maximum, Time to Maximum, Time to Half-Maximum will be set as missing. We will consider these variable as undefined.
 - b. The AUC_{0-t} will be calculated but the $AUC_{0-\infty}$ will be set as missing.
3. Multi-peak.
 - a. If the same Maximum value appears at two or more time point, the Time to Maximum, Time to Half-Maximum will be estimated based on the first occurrence.

All of the following GIR and PK parameters, including the primary variable, will be calculated after this data handling.

4.3.2.2 Handling of (Possible) non-response (0) GIR or Insulin Curve.

It is possible that some subjects do not respond to the bolus insulin which resulted in all GIR to be 0 or Insulin to be 0. In such case, the derived variable of this GIR / Insulin profile will be censored out from all analyses.

4.3.2.3 Variables for Primary Efficacy: Area Under the Curve (AUC) of the Glucose Infusion Rate (GIR)

The variable for Primary Efficacy is the AUC_{0-300} . It is estimated using the methods described in the following section 4.3.2.3.3.

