4.3.2.3.3 AUC_{0-t}

The AUC_{0-t} of GIR over wear time will be calculated using trapezoid rule and the actual time points. Missing data for the calculation of the AUC will be handled as followed:

1. If the reading for Time 0 is missing, it will be the average of up to 3 prior readings. However, if there is no prior readings available, it will be assumed to be 0
2. If the reading at (actual) time t ($t < 300$ min) is missing, it will be imputed with linear interpolation
3. If the reading at $t=300$ min is missing:
 - a. The reading at $t=300$ min will be imputed using the regression line obtained when estimate λ (section 4.3.2.3.1).
 - b. If λ is missing, AUC_{0-t} will be set as missing.

4.3.2.3.4 $AUC_{0-\infty}$

$AUC_{0-\infty}$ is estimated as

$$AUC_{0-\infty} = AUC_{0-last} + AUC_{last}, \text{ where } AUC_{last} = GIR_{last}/\lambda$$

If λ is missing, then $AUC_{0-\infty}$ is set as missing.

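### The SAP's terminal rate constant is fitted to every reading after the GIR peak, from as few as two points and with no limit on extrapolation, so AUC0-∞ carries an error that depends on peak time and curve shape

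*SAP*

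**What the plan says.** SAP 4.3.2.3.2 gives three steps for lambda: "Find the GIRs after" GIRmax, then "Do a regression of log-transformed GIR vs Time", and lambda "is the slope from this regression". No terminal portion of the curve is selected. Lambda is missing in a no-peak case, or under the condition "If there only 1 or 0 available GIR reading after" the maximum; otherwise any fit is accepted.

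SAP 4.3.2.3.4 adds a tail to the observed area, "AUC_{last} = GIR_{last}/\lambda". It gives no goodness-of-fit rule, no limit on the extrapolated share, and no definition of the last reading. SAP 4.3.2.3.6 also uses lambda, for a baseline-adjusted AUC0-∞.

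Three other places set the reach of the issue:
- SAP 4.3.2 states: "The variable for Primary Efficacy is the AUC_{0-300", so AUC0-∞ is not primary.
- The Protocol Synopsis (Secondary Endpoints 1) lists partial GIR areas "both absolute and as a percentage of total" AUC0-∞, but SAP 4.3.2.4.5 divides by AUC0-300.
- SAP 4.4.4.2.3 tests AUCs for treatment effects without saying whether AUC0-∞ is among them.

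**The concern.** A terminal rate constant should describe the final log-linear decline. On a smooth single-peaked curve the log slope is zero at the peak, so readings just after it are flatter than the decline that follows. Including them pulls the fitted slope away from the slope at 300 minutes, and the tail GIR_last/lambda inherits the error. The later the peak, the larger the share of post-peak readings that lie near it, and the more area has to be extrapolated.

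The timing of insulin action is itself under study: time to maximum GIR and the half-maximal times are endpoints, and the protocol's background describes faster absorption with wear. If timing differs between sets or days, an error tied to timing can appear as a difference in total effect. SAP 2.5 reports termination after the seventh subject completed, so one extreme extrapolated value could dominate a mean.

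**Working it through.** The documents give no value for lambda, AUC0-∞ or the extrapolated share, so there is no stated figure to reproduce. The check applies the SAP rule to curves whose true area is known.

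**Inputs.** Time grid from Protocol 6.1.1.5, taken as the GIR grid: every 5 min to 60 min, then every 10 min to 300 min. Fit and tail rules from SAP 4.3.2.3.2 and 4.3.2.3.4. The shape of the GIR curve is an assumption, because the documents give neither shape nor peak time.

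**Assumed curve.** G(t) = 500·k³·t²·exp(-kt) with k = 2/t_peak. Total area is 1000 for every peak time, and there is no noise. The true tail beyond 300 min is 1000·exp(-x)·(1 + x + x²/2) with x = 300k.

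**Rule, sign corrected.** Least squares of ln G on t over all grid points after the peak; lambda = minus the slope; tail = G(300)/lambda; AUC0-∞ = trapezoid area to 300 min + tail.

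| Peak (min) | AUC0-300 | G(300) | lambda (/min) | Tail by rule | True tail | AUC0-∞ by rule | Error | Extrapolated share |
|---|---|---|---|---|---|---|---|---|
| 90 | 961.5 | 0.628 | 0.01160 | 54.2 | 38.0 | 1015.7 | +1.6% | 5.3% |
| 110 | 908.3 | 1.157 | 0.00823 | 140.5 | 91.2 | 1048.8 | +4.9% | 13.4% |
| 130 | 838.6 | 1.622 | 0.00601 | 270.1 | 161.0 | 1108.7 | +10.9% | 24.4% |
| 150 | 761.5 | 1.954 | 0.00445 | 439.4 | 238.1 | 1201.0 | +20.1% | 36.6% |
| 180 | 647.0 | 2.202 | 0.00285 | 772.9 | 352.8 | 1419.9 | +42.0% | 54.4% |

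(Tails use unrounded lambda.) The mechanism shows in the slopes. The true log slope is 2/t - k. For the 110-min peak it is -0.01152 at 300 min, against a fitted -0.00823; for the 150-min peak it is -0.00667, against -0.00445.

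**Effect on a comparison.** Two curves of equal true area, peaking at 150 and 110 min, give 1201.0/1048.8 = 1.145, an apparent difference of about 14%.

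**Dependence on shape.** A gamma curve of shape 2 peaking at 120 min gives +20.0%, against +7.5% for shape 3 at the same peak. Bateman curves (two-rate absorption and elimination) give +0.4% to +5.4%. A fast-then-slow biexponential decline reverses the direction: area to 300 min 243.4, G(300) 0.228, lambda 0.00879, so 243.4 + 25.9 = 269.3 against a true 300.5, or -10.4%.

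**Lambda as printed.** The raw slope of a falling curve is negative, so the printed formula subtracts the tail: 908.3 - 140.5 = 767.8 (-23.2%) at a 110-min peak, and 761.5 - 439.4 = 322.1 (-67.8%) at 150 min.

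**Two-point fit.** With the peak at 280 min and readings of 3.9 and 3.8 mg/kg/min at 290 and 300 min, lambda = ln(3.9/3.8)/10 = 0.002598 per min, and the tail is 3.8/0.002598 = 1,463 mg/kg. With complete readings this needs a peak at exactly 280 min, so it shows that the rule has no floor; it is not a typical case.

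**Reach to the primary variable.** If the final readings are missing and the 300-min value is imputed from the regression line, AUC0-300 on the gamma curve (peaks 60 to 180 min) changes by at most 0.10% (last reading missing), 0.5% (last three) or 1.7% (last six). The largest shift in ln AUC is 0.017.

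**The case against.** The strongest objection is that little depends on AUC0-∞. The primary variable is AUC0-300, lambda touches it only when the 300-minute reading is missing, and the effect is then negligible. The SAP's percentage endpoint uses AUC0-300, and no test of AUC0-∞ is named. The trial stopped early and the SAP expects some outputs to be empty. All of this stands, and it keeps the point secondary. It does not remove it: AUC0-∞ is still derived, it is the percentage denominator in the protocol, and it may fall under the AUCs that are tested.

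A reader might also infer more than the documents support:
- **That AUC0-∞ is always overstated.** As printed, the tail is subtracted and AUC0-∞ is too small. With the sign corrected, the direction depends on shape. If GIR has returned to 0 by 300 min, which Protocol 6.1.1.5 allows, the tail is 0 when last means the 300-min reading, and the logarithm in the regression is undefined.
- **That the method favours one device.** No passage says which set acts more slowly or gives a GIR peak time. A distortion needs a timing difference, which is not established.
- **That the early share of effect is understated for a slower set.** This would follow from the protocol's denominator but not from SAP 4.3.2.4.5, where lambda enters only by imputing a missing 300-min reading.

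**Conclusion.** The flaw in the rule is certain from the text: a constant described as terminal is fitted to the whole post-peak curve, two readings are enough, and extrapolation has no limit. Its size is conditional. With the sign of lambda corrected and a decline that steepens after the peak, AUC0-∞ is overstated by about 5% at a 110-min peak and 20% at 150 min on the assumed gamma curve. With a fast-then-slow decline it is understated, by about 10% in the case tried. These figures rest on assumed, noise-free shapes and on taking the glucose sampling grid as the GIR grid.

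The consequence is limited to AUC0-∞ and its baseline-adjusted version. For the latter, this takes SAP 4.3.2.3.6 to intend that the whole difference GIR_last - GIR_0 be divided by lambda; as printed, only GIR_0 is. The point merits correction before these parameters are compared between sets or days, but it does not threaten the primary analysis.

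**What to change.** In SAP 4.3.2.3.2, define lambda as minus the slope, fitted to a prespecified terminal segment of the last positive, declining readings (at least three, for example the last three to six). Set lambda to missing if the slope is not declining. In 4.3.2.3.4, state which reading counts as last, including when GIR has returned to 0. Report the extrapolated share for each clamp, and flag AUC0-∞ or set it to missing above a stated share. Report the number missing by set and day, with AUC0-300 alongside as the main PD area.

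On the gamma curve the last six readings (250 to 300 min) reduce the error from +4.9% to +1.5% at a 110-min peak and from +20.1% to +8.5% at 150 min. The last three give +6.5% at 150 min and +17.0% at 180 min. The segment alone is therefore not enough for late peaks, and the limit on extrapolation is also needed. At a 150-min peak the extrapolated share is still 29.8% with the last six, so a 20% limit, for instance, would return missing there.

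Do not also require that terminal readings lie below half of GIRmax. At a 150-min peak GIR is still 73% of its maximum at 250 min and 54% at 300 min, so no reading would qualify.

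The cost is SAP wording and a short code change. AUC0-∞ will be noisier and more often missing for late-peaking clamps. That missingness depends on speed of action and is not random, so comparisons of AUC0-∞ should be labelled descriptive.

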4.3.2.3.3 AUC_{0-t}

The AUC_{0-t} of GIR over wear time will be calculated using trapezoid rule and the actual time points. Missing data for the calculation of the AUC will be handled as followed:

1. If the reading for Time 0 is missing, it will be the average of up to 3 prior readings. However, if there is no prior readings available, it will be assumed to be 0
2. If the reading at (actual) time t ($t < 300$ min) is missing, it will be imputed with linear interpolation
3. If the reading at $t=300$ min is missing:
 - a. The reading at $t=300$ min will be imputed using the regression line obtained when estimate λ (section 4.3.2.3.1).
 - b. If λ is missing, AUC_{0-t} will be set as missing.

4.3.2.3.4 $AUC_{0-\infty}$

$AUC_{0-\infty}$ is estimated as

$$AUC_{0-\infty} = AUC_{0-last} + AUC_{last}, \text{ where } AUC_{last} = GIR_{last}/\lambda$$

If λ is missing, then $AUC_{0-\infty}$ is set as missing.

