The run-in period should last no longer than 3.5 hours, if BG is not stable after this time, the participant cannot continue in the study and is sent home. He/she may return another day. Once the BG level of approximately 95 ± 15 mg/dL has been maintained for at least 40 minutes (measured every 10 minutes), the IV insulin (dextrose) is discontinued, and the baseline will be recorded for 20 min (blood draw every 5 min). 20 minutes after discontinuation of IV insulin, a SC bolus of lispro insulin (0.15 U/kg) is administered via the pump (t0). Baseline plasma glucose level is defined as mean plasma glucose at time points t-20, t-15, t-10, t-5, and t0. After t0, blood samples for PK analysis are drawn every 3 minutes for 15 min (Clamp Part I), every 5 minutes for 40 minutes (Clamp Part II), every 10 min for 30 min (Clamp Part III), and every 15 minutes for 45 minutes. In the Final Phase, blood is drawn every half an hour until clamp termination at 300 minutes (see Table 6). Up to 15 blood samples will be obtained overnight prior to the day of the glucose clamp procedure, and 8 additional blood samples will be obtained during stabilization on the morning of the clamp procedure prior to administration of the insulin bolus. Blood samples for immediate glucose determination will be drawn every 5 minutes for 60 minutes following insulin bolus, and then every 10 minutes for the remainder of the clamping period at 300 minutes post-bolus. Blood samples will be acquired using aseptic technique and double stopcock technique to minimize blood loss. A maximum of 66 samples (24 x 1.5 mL [for BG and insulin] + 6 x 1.0 mL [for PK only] + 36 x 0.5 mL for BG only = 62.0 mL) will be drawn during the stabilization period and the clamp procedure, resulting in a total blood loss of 248 mL during 4 clamps over each week. Combining both

clamping weeks, this represents less than 1 unit of blood (=525 mL). Blood samples will be centrifuged to plasma, plasma glucose concentration measured, and plasma frozen in 2 aliquots for future measurement of insulin concentration. The detailed clamp sampling schedule is summarized in Table 6.

Table 6. Clamp visit sampling schedule

Phase	Approximate Clock Time (hh:mm)	Nominal Time (min)	No. of samples	Volume/Sample (mL)	Total Volume (mL)
Stabilization, over night			15	0.5	7.5
Baseline Part I	7:00	-60	5	0.5	2.5
	7:10	-50		0.5	
	7:20	-40		0.5	
	7:30	-30		0.5	
	7:40	-20		0.5	
Discontinue IV insulin & Dextrose					

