Baseline Part II	7:45	-15	3	1.5	4.5
	7:50	-10		1.5	
	7:55	-5		1.5	
Bolus	8:00	0	1	1.5	1.5
Clamp Part I	8:03	3	7	1	6.5
	8:05	5		0.5	
	8:06	6		1	
	8:09	9		1	
	8:10	10		0.5	
	8:12	12		1	
	8:15	15		1.5	
Clamp Part II	8:20	20	9	1.5	13.5
	8:25	25		1.5	
	8:30	30		1.5	
	8:35	35		1.5	
	8:40	40		1.5	
	8:45	45		1.5	
	8:50	50		1.5	
	8:55	55		1.5	
	9:00	60		1.5	
Clamp Part III	9:10	70	3	1.5	4.5
	9:20	80		1.5	
	9:30	90		1.5	
Clamp Part IV	9:40	100	10	0.5	8.0
	9:45	105		1	

Phase	Approximate Clock Time (hh:mm)	Nominal Time (min)	No. of samples	Volume/Sample (mL)	Total Volume (mL)
	9:50	110		0.5	
	10:00	120		1.5	
	10:10	130		0.5	
	10:15	135		1	
	10:20	140		0.5	
	10:30	150		1.5	
	10:40	160		0.5	
	10:50	170		0.5	
	11:00	180		1.5	
	11:10	190		0.5	
	11:20	200		0.5	
	11:30	210		1.5	
	11:40	220		0.5	
	11:50	230		0.5	
Final Phase	12:00	240	13	1.5	11.5
	12:10	250		0.5	
	12:20	260		0.5	
	12:30	270		1.5	
	12:40	280		0.5	
	12:50	290		0.5	
	13:00	300		1.5	
Observation at site			66 total samples		
				Total volume per clamp =	62.0 mL

During the 5-hour clamp plasma glucose concentration will be maintained at 95 ± 15 mg/dL with IV infusion of dextrose (0.1 to 4 mg/kg/min), titrated using a computerized dosing algorithm according to frequent BG measurements. The trigger plasma glucose concentration for onset of glucose infusion will be a value that is 5 mg/dL below the mean obtained during Baseline Part II (i.e. -15, -10 and -5 minutes before bolus delivery at T=0). The dosing calculator will be used to determine the optimal glucose infusion rate (GIR) for each subsequent time period between BG measurements. If insulin is infused, glucose infusion must be stopped and vice versa. The dextrose infusion rate will be increased to match insulin lispro's glucose lowering effect over time until the glucose lowering effect of the insulin lispro bolus reaches baseline (i.e. glucose infusion rate of 0) or 5 hours after bolus administration.

In the case of persistent hyperglycemia (BG > 250 mg/dL) over 30 minutes without dextrose infusion, the clamp will be terminated early. A correction bolus will be given via the pump and the BG measured to determine whether BG was lowered by 50 mg/dL within 1 hour. If this is not the case, the CSII catheter is

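### When a clamp is stopped for hyperglycemia with dextrose already off, the SAP's 300-minute imputation adds glucose infusion that was not given to the primary AUC0-300

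*SAP*

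**What the plan says.** SAP 4.3.2.3.2 estimates the terminal rate constant λ from the readings after GIRmax: "Do a regression of log-transformed GIR vs Time". It gives no rule for zero readings. λ is missing in a no-peak case, or "If there only 1 or 0 available GIR reading after" the maximum; that count does not exclude zeros.

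SAP 4.3.2.3.3 then sets three rules for missing readings in the trapezoidal AUC:
- Rule 1 covers time 0.
- Rule 2 fills any gap before 300 minutes by linear interpolation.
- Rule 3 covers the 300-minute reading, which "will be imputed using the regression line obtained when estimate" λ. If λ is missing, so is the AUC.

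SAP 4.3.2.2 removes a profile only when every GIR is 0.

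Protocol 6.1.1.5 plans each clamp to 300 minutes but has an early stop. With blood glucose above 250 mg/dL "over 30 minutes without dextrose infusion, the clamp will be terminated early".

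**The concern.** A hyperglycemia stop is not an ordinary gap. The protocol's own condition means that no dextrose was running, so GIR at the stop is an observed 0. The imputation does not use that fact. It fits only the positive readings from before the effect ended, carries that line to 300 minutes, and joins the observed 0 to the result. The clamp ends up with a rising line of dextrose that nobody infused.

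Nothing else in the SAP catches this:
- The all-zero rule does not apply to a clamp with some positive GIR.
- The missing-λ rule does not apply once a line can be fitted.
- The sensitivity analysis in SAP 4.4.4.1 deals with missing AUC assessments, and an imputed AUC is not missing.
- The baseline-adjusted AUC subtracts only GIR at time 0 multiplied by time, so the added area stays in.

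The quantity affected is ln(AUC0-300 GIR), on which the treatment slopes are compared. The clamps affected are those in which insulin had stopped working.

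**Working it through.** The documents state no figure for this rule and give no GIR curves, so the profiles below are assumptions. The rule itself is applied literally.

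**Inputs from the documents**
- Reading times: every 5 minutes to 60 minutes, then every 10 (Protocol 6.1.1.5).
- Dextrose range: 0.1 to 4 mg/kg/min (same section).
- Clamp days: 0, 3, 5 and 7.
- Planned slope difference: 0.07 (SAP 3.4), taken as per day.
- Participants: 24 planned (SAP 3.4); terminated after the 7th completer (SAP 2.5).

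**Formulas**
- Fit ln(GIR) = a + b·t by least squares to the positive readings after the maximum.
- Imputed GIR300 = exp(a + 300b), which is always above 0.
- With a last reading of 0 at t_stop, added area = 0.5 × GIR300 × (300 − t_stop).

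**Stop at 190 minutes, so added area = 55 × GIR300**

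| Assumed GIR (mg/kg/min) | Observed AUC | b per min | GIR300 | Added area | Change |
|---|---|---|---|---|---|
| 0.5 from 30 to 100 min, then 0 | 38.75 | 0 | 0.500 | 27.5 | +71% |
| Rises from 20 min to 1.5 at 40, falls linearly to 0.7 at 140, 0 from 150 | 128.5 | −0.0075 | 0.219 | 12.1 | +9.4% |
| Rises from 20 min to 1.5 at 60, falls linearly to 0.7 at 140, 0 from 150 | 121.5 | −0.0098 | 0.151 | 8.3 | +6.8% |
| Rises from 20 min to 0.8 at 60, falls linearly to 0.3 at 120, 0 from 130 | 50.5 | −0.0172 | 0.0143 | 0.79 | +1.6% |

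In the flat case the observed area is 1.25 (25 to 30 min) + 35 (30 to 100) + 2.5 (100 to 110) = 38.75. It becomes 66.25, and ln(66.25/38.75) = 0.536. A steeper fall adds almost nothing.

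**Rising readings.** Suppose the only positive post-peak readings are 0.2 at 30 minutes and 0.3 at 40. Then b = ln(1.5)/10 = 0.0405 and GIR300 = 0.3 × exp(0.0405 × 260), or about 11,000 mg/kg/min. The rule has no check on the sign of the slope.

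**Effect on the slope**
- The mean day is 3.75 and the sum of squares is 14.0625 + 0.5625 + 1.5625 + 10.5625 = 26.75.
- The Day 7 weight is 3.25/26.75 = 0.1215. The Day 0 weight is −3.75/26.75 = −0.140.
- One flat clamp on Day 7: 0.536 × 0.1215 = +0.065/day in that participant's slope for that set.
- In the treatment mean: 0.065/7 = 0.009/day (13% of 0.07), or 0.065/24 = 0.003/day (4%).
- The same clamp on Day 0: 0.536 × (−0.140) = −0.075/day in that participant's slope, or −0.011/day averaged over 7. The decline becomes steeper.

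**The case against.** The strongest reply is that the trigger is narrow and the usual effect small. Much of this stands.

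- **A stop at 190 minutes is demanding.** Blood glucose must exceed 250 mg/dL from about 160 minutes. From the top of the clamp range (95 + 15 = 110 mg/dL) that is a rise of 140 mg/dL. In the flat case there are 60 minutes for it, or 2.3 mg/dL per minute. In the two profiles still at 0.7 at 140 minutes there are only 20, or 7 mg/dL per minute, which is hard to credit. Moving those two stops to 240 minutes allows 70 minutes (2 mg/dL per minute) and cuts the added area to 30 × GIR300, or +5.1% and +3.7%.
- **The flat case is the only large one with a non-rising line.** It needs a fitted slope near 0.
- **The rule may not be invoked.** If the site records GIR as 0 up to 300 minutes after a stop, nothing is imputed. The documents do not say whether it does.

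Three stronger readings are tempting, and the documents do not support them.

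- **That one bad clamp nearly cancels the planned effect.** The 0.065/day belongs to one participant and one set, while 0.07 is a difference in population mean slopes (Protocol 9.1, SAP 3.4).
- **That every clamp whose GIR returns to 0 is affected.** Dextrose is titrated until the effect "reaches baseline (i.e. glucose infusion rate of 0) or 5 hours after bolus administration", but that describes the infusion rate. The same section says "blood is drawn every half an hour until clamp termination at 300 minutes", so a normal clamp should have a recorded 0 at 300 minutes.
- **That the bias always flattens the decline.** Protocol 2.3.3 reports that 15% of Teflon sets in the cited steel-versus-Teflon trial kinked on insertion and were found within hours, although it expects less kinking with the control set used here. A Day 0 stop steepens the slope.

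**Conclusion.** The defect is real but limited. Followed as written, the SAP adds positive area to the primary AUC0-300 of any clamp that had some positive GIR, was stopped for hyperglycemia with dextrose off, has no 300-minute reading, and allows a line to be fitted. On the assumed profiles the addition is about 2-10% for declining readings, about 70% for flat ones, and unbounded for rising ones. A single flat clamp moves the treatment mean slope by about 0.009/day with 7 participants or 0.003/day with 24.

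The direction depends on the wear day of the stop, and which set benefits depends on where the stops fall. The documents settle neither. With so few participants one clamp can still matter, and a short rule removes the problem. The sizes rest on assumed curves and stop times; the sign of the added area does not.

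**What to change.** In SAP 4.3.2.3.3:
1. If a clamp ended early and GIR was 0 (dextrose off) at the stop, set GIR to 0 from the stop to 300 minutes and do not use the regression.
2. Use the regression only for readings missing for technical reasons, and only when it has at least two positive post-peak readings and a negative slope. Otherwise set AUC0-300 to missing.
3. List every clamp with imputed area, by set and wear day.

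In SAP 4.3.2.3.2, say that zeros do not enter the log regression and base the missing-λ count on positive readings.

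The cost is a few lines of text and code. The stop time and last GIR must be taken from the clamp record. Protocol 7.1.1 documents the reason for changing an infusion set, but the documents do not show that the reason for ending a clamp is captured, so telling technical gaps from other stops may need a check of source records. A few technically lost clamps will become missing in an already small trial. Setting GIR to 0 also assumes that the study bolus would have required no dextrose after the stop, which is weakest for very early stops; the listing lets a reader judge those.

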4.3.2.5 PK Parameters

4.3.2.5.1 AUC_{0-t}

AUC_{0-t} is calculated using the same methods as described in section 4.3.2.1.

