4.3.2.5.7 Time-to-Maximum Insulin Concentration (T_{max})

T_{max} will be calculated with the same methods as described in section 4.3.2.4.1.

- If C_{max} is missing, $t_{max(GIR)}$ will also be set as missing.

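### SAP 4.3.2.3.3 rule 3b, read literally, deletes fully observed early GIR AUCs when the 300-minute reading and λ are both missing; for still-rising curves it also conflicts with 4.3.2.1 rule 2b (minor)

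*SAP*

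**What the plan says.** **AUC rules (SAP 4.3.2.3.3).** AUC0-t of GIR "will be calculated using trapezoid rule and the actual time points". If a reading before 300 min "is missing, it will be imputed with linear interpolation" (rule 2). If the 300-minute reading is missing, it is imputed from the regression that gives λ (rule 3a). Rule 3b then adds: "If λ is missing, AUC_{0-t} will be set as missing".

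**When λ is missing (SAP 4.3.2.3.2).** There are two conditions. The first begins "If there only 1 or 0 available GIR reading after" GIRmax. The second is "In a “No Peak” case, λ will be set as missing". The same section introduces λ as a quantity required before AUC0-t is estimated.

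**No-peak curves (SAP 4.3.2.1 rule 2).** The case is defined as "No peak. (i.e. the variables keeps rising up to 300 minutes", judged by eye from the plot. Rule 2b says that AUC0-t is calculated for such a curve and only AUC0-∞ is set to missing. The section states that its handling precedes all later GIR and PK parameters, the primary variable included.

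**Endpoints concerned (Protocol 1.1, Secondary Endpoints 1).** AUC0-t of GIR at 14 times: 5, 10, 15, 20, 30, 45, 60, 90, 120, 150, 180, 210, 240 and 300 min.

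**Insulin Tmax (SAP 4.3.2.5.7).** If insulin Cmax is missing, the GIR tmax "will also be set as missing". SAP 4.3.2.4.1 already ties the GIR tmax to GIRmax.

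**The concern.** A trapezoidal AUC to 60 min uses readings up to 60 min. It cannot depend on a reading at 300 min or on a terminal slope fitted after the peak. Rule 3b nevertheless makes every AUC0-t depend on both. A program written from the text would blank partial AUCs for which all the data exist.

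The deletion is triggered partly by curve shape, because λ is missing when the peak comes late or not at all. It is therefore related to the outcome rather than to chance. The trial stopped after its seventh completer (SAP 2.5), which gives at most 7 × 2 periods × 4 clamps = 56 clamps from completers, so values should not be lost without reason.

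For a no-peak curve without a 300-minute reading, the SAP also gives two opposite instructions. That covers AUC0-300, the variable behind the primary endpoint.

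**Working it through.** The plan states no figure for this point, so there is nothing to reproduce. The check applies the rules as written to example curves.

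**Inputs**
- Reading times: the glucose schedule in Protocol 6.1.1.5, every 5 min to 60 min and then every 10 min to 300 min. I assume that GIR readings follow it. All 14 AUC times lie on this grid.
- Missing data: the 300-minute reading only.
- Curve shape (assumed for illustration): linear rise from 0 to 6 arbitrary units at the peak, then exponential decay.
- λ is missing if there are 0 or 1 readings after GIRmax, or no peak (SAP 4.3.2.3.2).

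**Result of the literal rule**

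| Peak at | Readings after peak | λ | AUC0-t for t < 300 observed | AUC0-t for t < 300 kept under rule 3b |
|---|---|---|---|---|
| 150 min | 14 (160 to 290) | available | 13 | 13 |
| 280 min | 1 (290) | missing | 13 | 0 |
| 290 min | 0 | missing | 13 | 0 |

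**What is discarded.** On the rising limb, AUC0-t = ½ × t × (6t / peak time).
- Peak at 280 min: AUC0-60 = ½ × 60 × (6 × 60 / 280) = 38.6, and AUC0-240 = ½ × 240 × (6 × 240 / 280) = 617.1.
- Peak at 290 min: AUC0-60 = ½ × 60 × (6 × 60 / 290) = 37.2, and AUC0-240 = ½ × 240 × (6 × 240 / 290) = 595.9.

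None of these uses λ or the 300-minute value. The literal rule returns missing for all of them. The baseline-adjusted AUC0-t (SAP 4.3.2.3.5) is computed from AUC0-t and is lost with it.

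**The conflict with 4.3.2.1 rule 2b.** Take the curve still rising at 290 min.
- If it is classed as no-peak, rule 2b says to calculate AUC0-t. SAP 4.3.2.3.2 makes λ missing for the same curve, so rule 3b says to set AUC0-t to missing. The two cannot both be followed.
- If it is not classed as no-peak, rule 2b is silent. λ is still missing because no reading follows the maximum, and rule 3b deletes all 14 values.
- The curve peaking at 280 min has a peak, so only rule 3b applies to it.

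**What is not wrongly deleted.** With the 300-minute reading absent and no λ, rule 3a cannot supply the endpoint of AUC0-300. Setting AUC0-300 to missing is then reasonable, as it is for the percentages of AUC0-300 and the duration of action, which divide by it.

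**The case against.** **The natural reading of rule 3b.** It is a sub-item of the rule for a missing 300-minute reading, and rule 2 deals separately with gaps before 300 min without λ. Read in place, it may mean AUC0-300 only. That is probably the intent. It is not what is written: the SAP names AUC0-300 when it means it (4.3.2.3, 4.3.2.4.4, 4.3.2.4.5), and 4.3.2.3.2 says λ is required for AUC0-t in general. A careful programmer could go either way.

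**The no-peak definition.** Rule 2b concerns curves that rise to 300 min, and rule 3b concerns curves with no reading there, so the two might never meet. This partly stands: the conflict arises only if a curve still rising at its last reading is classed as no-peak. That call is left to visual judgement, so it can happen.

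**Inferences that go further than the documents allow**
- *A clamp stopped early while GIR is rising loses its early AUCs.* The early-stop rule in Protocol 6.1.1.5 applies to persistent hyperglycaemia with no dextrose running. GIR is then zero, so the documents give no cause for a rising GIR curve cut off at, say, 120 min.
- *The PK AUCs and early insulin exposure are lost too.* SAP 4.3.2.5.1 says the PK AUC0-t "is calculated using the same methods as described in section 4.3.2.1", not 4.3.2.3.3, and 4.3.2.1 says AUC0-t is calculated for no-peak curves. The reference is probably stale, since 4.4.4.1 cites the same section for a trapezoidal rule that it does not contain. Carry-over is therefore possible but uncertain. AUC0-60 has its own rule (4.3.2.5.3): it is calculated when the sample falls between 55 and 65 min.
- *Early-exposure comparisons are biased toward no difference.* That would require late-peaking curves with missing final readings to cluster in one infusion set. Nothing in the documents shows this.
- *Insulin Tmax has no missing-value rule.* SAP 4.3.2.5.7 imports the method of 4.3.2.4.1, which by analogy includes one.

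**Conclusion.** The point holds as a minor drafting error. Read literally, rule 3b removes up to 13 fully observed secondary PD partial AUCs from any clamp that lacks both the 300-minute reading and λ, and it contradicts rule 2b for curves classed as no-peak. The example counts rest on the assumed reading grid and on only the 300-minute reading being missing.

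Both conditions must occur together; with a peak at 150 min nothing is lost. The documents give no rate for missing 300-minute readings or for late peaks, so the frequency cannot be computed. It is probably low among at most 56 completer clamps, a ceiling that takes no account of early set failures.

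A reader might infer that the primary endpoint is wrongly deleted. It is not, beyond the unresolved choice between the two rules for AUC0-300 in the no-peak case.

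The wrong variable in 4.3.2.5.7 is most likely a subscript slip. Coded literally it would discard a valid GIR tmax because of an insulin gap, so it should be corrected, but it carries little weight.

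**What to change.** 1. SAP 4.3.2.3.3 rule 3b: replace with wording such as: *If λ is missing, AUC0-t is set to missing only for t later than the last observed reading; AUC0-t for earlier t is calculated from the observed data.* When only the 300-minute reading is absent, this affects AUC0-300 and the quantities derived from it, and keeps the 13 earlier values.
2. State whether 4.3.2.1 rule 2b or 4.3.2.3.3 rule 3b governs AUC0-300 for a no-peak curve with a missing 300-minute reading. If rule 2b governs, say how the interval to 300 min is completed without λ.
3. SAP 4.3.2.5.1: point the PK AUC0-t to the section that holds the AUC method, so that it is clear whether the amended rule applies there.
4. SAP 4.3.2.5.7: replace the GIR tmax with the insulin Tmax.

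The cost is a few sentences in the SAP and matching derivation code, with no new data and no added analyses.
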